Diagnosis and Main Inclusion Criteria	Male and female adolescents (ages 12-18) will be eligible for the study if they completed acute phase treatment and showed at least a partial response to treatment (CGI-I of minimally improved or better (CGI-I \leq 3)). Adolescents will enter continuation treatment having either received 12 sessions of IPT-A, 16 sessions of IPT-A, or 12 sessions of IPT-A plus fluoxetine.
Study Product, Dose, Route, Regimen	Adolescents who received fluoxetine during the acute phase and were responders (CGI-I = much improved or very much improved (CGI-I = 1 or 2)) will continue their acute phase dosing regimen and will meet with the psychiatrist on a monthly basis. Adolescents who received fluoxetine during the acute phase and were partial responders (CGI-I = minimally improved (CGI-I = 3)) will enter the continuation phase on 40mg fluoxetine, and will have their dose increased to 60mg. Adolescents who received only IPT-A during acute phase and were partial responders (CGI-I = minimally improved (CGI-I = 3)) will begin treatment with fluoxetine, in addition to continuing their IPT-A treatment. The dosage schedule will be 10mg per day for the first week and 20mg per day for the following 5 weeks. If no treatment response is observed by the 6th week, the dosage can be increased to 40mg per day.¹⁵
Duration of administration	16 weeks
Reference therapy	Interpersonal Psychotherapy for Depressed Adolescents (IPT-A)

CONFIDENTIAL

This material is the property of the University of Minnesota. Do not disclose or use except as authorized in writing by the study sponsor

Statistical Methodology	

1. Mean [95% confidence interval] treatment satisfaction for each adaptive treatment strategy (ATS)
2. Mean therapy session attendance and dropout rates for each ATS.
3. Within-subject change scores in CDRS-R, SAS-SR, and CGAS scores for the early and late decision point groups from pre- to post-treatment using repeated measures ANOVA.
----------------------------	--

CONFIDENTIAL

1 Introduction

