1.1 Background

Adolescent depression is a prevalent and debilitating disorder that places youth at risk for suicidality, other psychiatric diagnoses, and significant psychosocial impairment both during adolescence and into adulthood.^{1,2} Research on the treatment of adolescent depression has dramatically increased over the past two decades. Two psychotherapies meet the American Psychological Association's criteria for "well-established" treatments (interpersonal psychotherapy and cognitive behavioral therapy).³ Fluoxetine, paroxetine, sertraline, and escitalopram also have demonstrated efficacy as pharmacological treatments.⁴⁻⁸ While the progress in this area has been substantial, the overwhelming majority of treatment studies have focused on the acute phase of treatment, that is, the phase of treatment focused on initial clinical response and remission of symptoms.⁹ However, among the acute treatment studies that have reported long-term follow-up data, 25-50% of the adolescents in these studies experienced a depressive relapse following the completion of treatment.¹⁰⁻¹³

The American Academy of Child and Adolescent Psychiatry Practice Parameter for the treatment of depression recommends providing continuation treatment following the symptom remission achieved during the acute phase of treatment.¹⁴ The goals of continuation treatment are to consolidate the acute phase treatment response and avoid relapse. Research on continuation phase treatment for adolescent depression is extremely limited, and as a consequence, this Practice Parameter was based primarily on adult treatment studies and clinical consensus.¹⁴ The handful of studies with adolescents that have examined postacute treatment have found that continuation treatment is associated with a decreased risk of relapse,^{11,15,16} and can facilitate further symptom reduction in adolescents who were partial responders to acute phase treatment.^{11,17}

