- Hypotheses 5 & 6: (1) Primary analyses will examine within-subject change scores in CDRS, C-SSRS and CGAS over the course of acute and continuation treatment using repeated measures analysis of variance (ANOVA). Linear regression and analysis of covariance (ANCOVA) adjusting for pre-treatment scores will also be used to analyze changes in adolescents' outcomes. The magnitudes of changes in outcomes variables over time will be assessed using the paired t-test or Wilcoxon signed-rank test for continuous variables. Mixed-effects regression models will also be employed to compare CDRS, C-SSRS, and CGAS scores over multiple time points in order to obtain information on specific patterns of change over time. (2) Secondary analyses comparing within-subjects change scores across treatment groups on self-report measures of depression (BDI-II) and functioning (CBQ, SAS-SR) will be conducted using two-sample t-test, Wilcoxon rank sum test, and linear regression analysis. Hierarchical linear modeling (HLM) will also be conducted to compare scores over multiple time points within each treatment group. (3) Recovery will be defined as an absence of depression symptoms on the KSADS-PL for at least 8 weeks. Relapse will be defined as the reemergence of 5 or more symptoms of depression on the KSADS-PL. The percentage of adolescents who meet recovery criteria, and associated 95% confidence interval will be calculated. The percentage of adolescents who meet relapse criteria, and associated 95% confidence interval will be calculated. For those with a relapse, the mean (SD) time from recovery to relapse will be calculated.

Exploratory Analyses: Exploratory analyses will be conducted to determine whether comorbid psychiatric disorders, baseline severity of depression, and different forms of functioning (CBQ, SAS-SR, CGAS) predict or moderate positive or negative treatment outcomes. Potential predictors and moderators will be used to refine the personalized treatment strategy that will be tested in the subsequent R01.

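### The primary analysis for Hypotheses 5 and 6 includes the acute-phase gain and is not split by acute response, CGI response status has no planned analysis, and the Study Summary and section 7.2 list different outcomes

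*Combined protocol and SAP*

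**What the plan says.** Section 2 separates two groups with two targets. Under Hypothesis 5, acute responders sustain their response; under Hypothesis 6, partial responders improve in depressive symptoms and in social and global functioning. Section 1.1 gives the purpose: "The goals of continuation treatment are to consolidate the acute phase treatment response and avoid relapse". Section 3.1 places entry to continuation at week 16, with assessments at weeks 24 and 32. Section 4.1 admits only adolescents with CGI-I of 3 or less after acute treatment.

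Section 7.2 handles the two hypotheses together:

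- Item (1), the primary analysis, is a repeated measures ANOVA of "within-subject change scores in CDRS, C-SSRS and CGAS over the course of acute and continuation treatment". It adds linear regression and "analysis of covariance (ANCOVA) adjusting for pre-treatment scores", and paired t or signed-rank tests of change over time. It also says "Mixed-effects regression models will also be employed to compare CDRS, C-SSRS, and CGAS scores over multiple time points".
- Item (2) covers the self-report scales (BDI-II, CBQ, SAS-SR), compares change between treatment groups and adds: "Hierarchical linear modeling (HLM) will also be conducted to compare scores over multiple time points within each treatment group".
- Item (3) defines recovery and relapse on the K-SADS-PL and states: "The percentage of adolescents who meet relapse criteria, and associated 95% confidence interval will be calculated".

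Section 7.2 opens by placing every analysis on the intent-to-treat sample, which section 7.1 sets at 30. Section 3.3 lists CGI response status as a secondary endpoint (1 or 2 is a responder, 3 a partial responder). Section 3.4 makes the C-SSRS a primary safety endpoint. Item 3 of the Statistical Methodology in the Study Summary names "CDRS-R, SAS-SR, and CGAS scores for the early and late decision point groups from pre- to post-treatment".

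**The concern.** Whether response is sustained is a question about what happens after week 16 in those who had responded by then. A change measured from before acute treatment adds the acute gain to the continuation change. Because entry depends on an acute improvement, the first part is favourable almost by construction. The total can therefore stay favourable when the second part is a loss. Combining responders, who are expected to hold, with partial responders, who are expected to improve, blurs it further.

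The share of responders who remain responders is the plainest summary of Hypothesis 5. It uses an endpoint that section 3.3 already lists, yet section 7.2 never mentions CGI.

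What is at stake is Aim 2, which is to estimate outcome variances for a later, larger proposal. The variance of a full-span change is not the variance of a continuation change. The conflicting outcome lists also leave open whether social functioning, named in Hypothesis 6, belongs to the main set. They leave the C-SSRS summarised only as a score change, with no planned count of adolescents with ideation or behaviour.

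**Working it through.** **Text check: what each analysis gives for Hypothesis 5**

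| Element of 7.2 | Starts at week 16? | Split by acute response? | Outcome |
|---|---|---|---|
| (1) ANOVA | No, spans acute and continuation | No | CDRS, C-SSRS, CGAS |
| (1) ANCOVA | Pre-treatment score not defined as pre-acute or week 16 | No | Adolescents' outcomes, not named further |
| (1) Paired tests, mixed models | Possible, not specified | No | Mixed models: CDRS, C-SSRS, CGAS; paired tests: outcomes not named |
| (2) Group comparisons, HLM | Not specified | Partly, since 5.3 bases groups on CGI-I | Self-report scales only |
| (3) Recovery, relapse | Not applicable | No | K-SADS-PL, intent-to-treat sample |
| CGI response status | Absent | Absent | Absent |

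Relapse needs five or more K-SADS-PL symptoms to re-emerge. A responder who slips from CGI 2 to 3 or 4 below that threshold is not counted.

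**Outcome lists.** Study Summary: CDRS-R, SAS-SR, CGAS. Section 7.2(1): CDRS, C-SSRS, CGAS. The SAS-SR is secondary in 7.2(2); the C-SSRS is a safety endpoint in 3.4.

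**Numerical illustration.** The sample size of 30 has no formula behind it, so there is no stated figure to reproduce. The documents give no effect sizes, SDs or responder counts, so all of these are assumed. The unit is the SD of a paired change, taken as equal for both spans. The number of responders n runs from 10 to 25.

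*Step 1: full-span change.* Net change = acute gain − later loss = 1.5 − 0.5 = 1.0 SD, still an improvement. The probability that a two-sided 0.05 paired t-test shows significant improvement is P(T > t(0.975, n−1)), where T is noncentral t with n−1 degrees of freedom and noncentrality 1.0 × √n:

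- n = 10: 0.80; n = 15: 0.95; n = 20: 0.99; n = 25: above 0.99.
- At n = 20 with the same 0.5 SD loss: an acute gain of 1.0 SD (net 0.5) gives 0.56; a gain of 2.0 SD (net 1.5) gives above 0.99.
- At n = 20 with a gain of 1.5 SD: a loss of 0.25 SD gives above 0.99; a loss of 0.75 SD gives 0.89.

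*Step 2: overall ANOVA time effect.* Simulated with 20,000 runs, four visits (pre-acute and weeks 16, 24, 32), visit SD 1, correlation 0.5 (so a paired change has SD 1), a 1.5 SD gain, and half of any loss occurring by week 24. The effect is significant with probability 1.000 if the gain is held and 1.000 if 0.5 SD is lost at n = 20, and 0.998 and 0.986 at n = 10. The overall test does not tell the two cases apart.

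*Step 3: change from week 16.* The 95% CI half-width is t(0.975, n−1)/√n. At n = 20 it is 2.093/4.472 = 0.47 SD. It is 0.72 at n = 10, 0.55 at n = 15 and 0.41 at n = 25. The test of a 0.5 SD loss has noncentrality 0.5 × √n and detects it with probability 0.29 (n = 10), 0.44 (15), 0.56 (20) and 0.67 (25).

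*Step 4: proportion still at CGI-I 1 or 2.* Exact (Clopper-Pearson) 95% intervals if 80% stay responders: 8/10, 44% to 97%; 12/15, 52% to 96%; 16/20, 56% to 94%; 20/25, 59% to 93%.

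**Are CGI ratings available?** CGI is not among the measures listed for the blind evaluators in 3.1. Section 8.4 has therapists rate CGI-I at every session. Taking a month as 4 weeks, the 3.1 schedule puts responder sessions at weeks 18, 20, 22, 24, 28 and 32, or at 16, 18, 20, 22, 26 and 30 if the first falls at week 16. Partial responders have sessions at weeks 17 to 24, 28 and 32, or 16 to 23, 27 and 31. With full attendance a session lies within about 2 weeks of weeks 24 and 32. In the second responder calendar, weeks 22 and 26 are equally near week 24.

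**The case against.** A reader might infer that section 7.2 offers nothing for Hypothesis 5, or that its analysis would hide a loss. The documents do not support that. The paired tests and mixed models in 7.2(1) are not limited to pre-acute against week 32, and fitted means at weeks 16, 24 and 32 would show a decline. Section 2 does not define sustained response as CGI-I 1 or 2, and avoiding relapse, which 7.2(3) estimates with an interval, is part of the purpose given in 1.1. Because 5.3 assigns treatment on CGI-I, the group analyses in 7.2(2) partly separate the response groups. The fault is that the needed contrast and split are not specified for CDRS and CGAS; an analyst could produce them, but nothing commits the analyst to do so.

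A reader might also infer that the relapse percentage has no denominator. It has one: the intent-to-treat sample, set at the start of 7.2. What is open is whether relapse is also to be shown among those who first recovered.

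Two further objections stand. A week-16 baseline asks the right question but has modest power at these numbers; at n = 10 the half-width (0.72 SD) exceeds the assumed loss. And session CGI-I ratings serve the proposed proportion only if they are anchored to the pre-acute state. Anchored to continuation entry, a stable responder would be rated as unchanged (4) and counted as a failure. The documents do not state the anchor.

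Finally, 7.1 disclaims any evaluation of efficacy. That limits the weight of the point, but a pilot that sets out to estimate variances still needs to estimate them for the intended quantity.

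**Conclusion.** The point holds as a gap in specification. The stated primary change for Hypotheses 5 and 6 includes the gain required for entry and is not split by acute response, so a favourable result cannot show that response was sustained. CGI response status has no planned analysis, and the outcome lists conflict.

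The size depends on assumed inputs. With a 1.5 SD gain, a 0.5 SD loss and 10 to 25 responders, the full-span paired test shows improvement with probability from 0.80 to above 0.99. With 20 responders and a gain of only 1.0 SD it falls to 0.56.

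The documents do not settle which outcome list was intended. The decision-point groups in the Study Summary are not defined in the available text, and the design figure is not shown, so the lists need reconciling rather than one being declared wrong. Nor should the C-SSRS point be read as a gap in individual protection: 8.4 provides for suicidality assessment at each session and review by the safety monitor.

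These are secondary outcomes in a 30-subject pilot. The primary feasibility and acceptability endpoint is unaffected. The plan should be amended, but the study is not undermined.

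**What to change.** (a) For Hypotheses 5 and 6, report change from week 16 to weeks 24 and 32 with 95% CIs, separately for acute responders and partial responders. Use the week-16 score as the ANCOVA covariate for these changes. Keep the full-span analysis as supportive.

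(b) Reconcile the outcome lists in the Study Summary, 3.3 and 7.2(1). Cover social functioning (SAS-SR) for Hypothesis 6, and summarise the C-SSRS as safety counts.

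(c) Report the proportion of week-16 responders still at CGI-I 1 or 2 at weeks 24 and 32, and of partial responders reaching 1 or 2, with exact 95% CIs, using ratings anchored to the pre-acute baseline. If the 8.4 session ratings are anchored to continuation entry, they cannot be used this way. If they are used, state that they are not blind, give a rule for ties in the nearest session, and add a sensitivity analysis counting missing ratings as not responding. For example, if 2 of 20 are unrated, 16/18 (89%, 65% to 99%) becomes 16/20 (80%, 56% to 94%).

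(d) Report recovery and relapse by acute-response group as well as in the intent-to-treat sample, and state whether relapse is also shown among those who met recovery.

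The cost is wording and a little more analysis. No new visit is needed, and no new rating if the session ratings prove to be anchored to the pre-acute baseline. The downside is low precision, so the results should be presented as estimates with intervals and not as tests of sustained response.

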possible that adolescents seeking treatment from a community clinic might be at a greater risk for clinical deterioration and might be less likely to demonstrate a clinical improvement than if they received the treatments provided in this study. What is experimental in this study is the criteria for initiating a change in the treatment plan, the timing of a potential change in the treatment plan, and the type of change to the treatment plan. Currently, there are virtually no empirically-derived guidelines to direct clinicians in deciding whether, when, or how to alter a treatment plan for adolescent depression. Consequently, we expect the relation of the anticipated benefits to the risks to be at least as favorable to the subjects as that presented by available non-study treatment.

2 Study Objectives

Aim 1: Assess the feasibility and acceptability of the personalized continuation treatment strategy.

- Hypothesis 1: Adolescents who responded to the acute phase treatment provided in the K23 study and their parents will consent to participate in continuation treatment.
- Hypothesis 2: Adolescents will be adherent to continuation treatment and will complete the continuation treatment protocol.
- Hypothesis 3: Adolescents and parents will report satisfaction with continuation treatment.
- Hypothesis 4: Treating clinicians will report satisfaction with continuation treatment.

Aim 2: Estimate variances of primary and secondary outcomes with the continuation treatment.

- Hypothesis 5: Adolescents who were responders to acute treatment will show sustained response to continuation treatment.
- Hypothesis 6: Adolescents who were partial responders to acute treatment will show significant improvement in depressive symptoms and social and global functioning.

Aim 3: Conduct exploratory hypothesis-generating analyses to inform further development of the personalized continuation treatment strategy to be tested in a subsequent R01 proposal.

3 Study Design

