7.2 Statistical Methods

All statistical analyses will be conducted on the intent-to-treat sample.

- Hypothesis 1: Among families in the acute phase study who are eligible to participate in continuation treatment, the percentage of adolescents and parents

CONFIDENTIAL

who consent to participate in the continuation treatment, and associated 95% confidence intervals will be calculated.

- Hypothesis 2: The mean/median (depending on the distribution) number and proportion of sessions attended by adolescents, as well as the associated 95% confidence intervals, will be calculated. The proportion of adolescents dropping out of treatment prematurely, and the associated 95% confidence interval, will be calculated.
- Hypothesis 3: An overall mean treatment satisfaction rating, and associated 95% confidence interval, will be calculated based on adolescents' and parents' responses on the CSQ-8.
- Hypothesis 4: An overall mean treatment satisfaction rating and the associated 95% confidence interval will be calculated based on clinicians' response on the clinician satisfaction measure.

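### Hypothesis 6 predicts significant improvement, but the primary analysis covers three unranked outcomes with several overlapping tests and names no contrast, decision rule or multiplicity rule

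*Combined protocol and SAP*

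**What the plan says.** Hypothesis 6 (section 2, Study Objectives) reads: "Adolescents who were partial responders to acute treatment will show significant improvement in depressive symptoms and social and global functioning". Hypothesis 5 concerns responders and predicts sustained response, not improvement.

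Section 7.2, item (1) for Hypotheses 5 and 6, states: "Primary analyses will examine within-subject change scores in CDRS, C-SSRS and CGAS over the course of acute and continuation treatment", with repeated-measures ANOVA as the method. It then adds:

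- "Linear regression and analysis of covariance (ANCOVA) adjusting for pre-treatment scores will also be used"
- "The magnitudes of changes in outcomes variables over time will be assessed using the paired t-test or Wilcoxon signed-rank test", with no rule for choosing between the two
- "Mixed-effects regression models will also be employed to compare CDRS, C-SSRS, and CGAS scores over multiple time points"

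The Study Summary names repeated-measures ANOVA only, for a different trio: "Within-subject change scores in CDRS-R, SAS-SR, and CGAS scores". There it compares early and late decision point groups. Section 3.3 lists CDRS, C-GAS, SAS-SR and CGI response as secondary endpoints. Section 3.4 makes suicidality on the Columbia scale a safety endpoint. Section 7.2 uses the intent-to-treat sample and section 7.3 refers to all populations; neither limits the test of Hypothesis 6 to partial responders.

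No significance level, sidedness or multiplicity rule is given. The nearest indication is that for Hypothesis 1 "associated 95% confidence intervals will be calculated".

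**The concern.** A hypothesis worded in terms of significance needs one identified test, or a rule for combining several. Here three outcomes share the label primary, each is analysed in up to four ways, and neither the contrast nor the decision rule is fixed. If one significant result is enough, Hypothesis 6 can be reported as supported more often than a single test would allow when nothing has changed.

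The outcomes also fit the hypothesis poorly. Hypothesis 6 names social functioning, but SAS-SR appears only among the secondary analyses of section 7.2. C-SSRS is in the primary list although suicidality is not part of the hypothesis.

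The time span is a second problem. Item (1) covers acute and continuation treatment together, while section 4.1 admits only adolescents rated at least minimally improved after the acute phase. A pre-to-post change over the whole span can therefore be significant even if continuation treatment adds nothing.

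**Working it through.** The documents give no error rate or power figure for Hypotheses 5 and 6, so there is no figure of theirs to reproduce. The sample of 30 is justified by feasibility (section 7.1).

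**Inputs from the documents.** Three outcomes and the listed methods (section 7.2). Entry at week 16 and assessments at weeks 24 and 32 (section 6). N = 30 in total (section 7.1). The number of partial responders is not given.

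**Assumptions.** Two-sided alpha 0.05, in line with the 95% intervals. Normal data with no true mean change. Sample sizes of 10 to 30. Correlation 0 to 0.7 between outcomes and 0.3 to 0.7 between visits, with 0.5 for both as the central case. Three visits, or four if an acute-phase baseline is added. Hypothesis 6 counts as supported if any one outcome is significant.

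**Step 1: reference values for independent tests.** Chance of at least one false positive = 1 − (1 − 0.05)^k.

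- k = 3: 1 − 0.95^3 = 14.3%
- k = 6: 1 − 0.95^6 = 26.5%
- k = 12: 1 − 0.95^12 = 46.0%

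The tests here are correlated, so 46.0% is not a fair estimate, and simulation is needed.

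**Step 2: simulation under no change.** Each outcome was tested by repeated-measures ANOVA, ANCOVA (change on centred baseline), paired t, Wilcoxon and a random-intercept slope model.

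| What is counted as a positive result | Either direction | Improvement only |
|---|---|---|
| One outcome, ANOVA only | 4.3-5.6% | about 2.5% |
| Three outcomes, ANOVA only | 10.6-14.6% | – |
| Three outcomes, paired t only | 10.9-14.8% | 5.5-7.3% |
| Three outcomes, all methods except ANCOVA | 19-28% | 10-15% |
| Three outcomes, all methods | 20-34% | 10-18% |

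In the central case with n = 30, the last two rows are 21% and 26% in either direction, and 11% and 13% for improvement. The highest values come from the ANCOVA intercept test, which treats the baseline mean as fixed, and from settings with weaker correlation.

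**Step 3: inflation for a false improvement.** 10 / 2.5 = 4 and 18 / 2.5 = 7.2, so roughly four- to seven-fold.

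**Step 4: effect of the decision rule.** Central case, best of ANOVA, paired t and slope:

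- any of three outcomes improves: about 10-11%
- either CDRS or CGAS improves, leaving C-SSRS out because suicidality is not in Hypothesis 6: about 8%
- CDRS and CGAS must both improve: about 1%

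The unstated rule moves the answer from about 1% to 10% or more, a larger effect than any of the assumed correlations.

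**Step 5: the time span.** These simulations assume no change at any visit. That null does not describe a span that includes acute treatment. Partial responders are by definition rated minimally improved over the acute phase (CGI-I of 3). CGI-I is not CDRS-R, but both follow the same clinical course, so an acute-phase gain in CDRS-R is to be expected. The rates above do not include this effect.

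**The case against.** The strongest reply is that a primary method is designated. Repeated-measures ANOVA is the one attached to the primary analyses and the only one in the Study Summary. The regression and mixed models are introduced as additions, and the paired tests as measures of magnitude. That stands: a reader might infer that no method was chosen, and the text does not support it. It does not settle Hypothesis 6, however. ANOVA alone on three unranked outcomes still gives about 11-15%, and an overall time test across three visits has no direction.

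A reader might also take 20-28% as the chance of a false improvement. It is the rate for a change in either direction; the improvement rate is about half. The upper part of that range also depends on added choices: a separate week 16 to week 24 contrast that the plan does not name gives 25-26%, and counting both paired tests where the plan offers one or the other gives 27-28%.

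Hypothesis 6 joins its domains with an and. Read as requiring all of them, the false-positive rate is very small. The documents do not say which reading applies, so this limits the size of the concern without removing it.

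Finally, section 7.1 disclaims evaluating efficacy, section 3.2 makes feasibility and acceptability primary, and Aim 2 is framed as estimating variances. A reader might infer that a false positive on Hypothesis 6 would be used to justify the later R01. Section 7.2 links only the predictor and moderator analyses to that proposal. These points lower the stakes. Even so, the Study Summary lists preliminary efficacy among the objectives, and Hypothesis 6 is worded as a significance claim.

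**Conclusion.** The concern holds in a limited form. The method is designated; the outcome, contrast, population, time span and decision rule for Hypothesis 6 are not, and multiplicity is not addressed. If any one outcome suffices at two-sided 0.05 with correlations of about 0.5, the chance of some false significant change is about 20-28%. The chance of a false improvement is about 10-18% over the range of correlations tried (11-13% in the central case), against 2.5% for one pre-named test. Alpha, correlations, normality, the number of partial responders and the any-one-outcome rule are all assumptions. Requiring both CDRS and CGAS to improve brings the rate to about 1%.

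Separately, and whatever the multiplicity, change measured across the acute phase cannot be read as a continuation benefit in patients selected for acute improvement. The consequence is moderate, and the text should be corrected.

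**What to change.** Rewrite item (1) of section 7.2 so that Hypothesis 6 rests on one result: the week 16 to week 32 change in CDRS-R among partial responders, from a single named repeated-measures model with week 16 as baseline, reported as an estimate with its 95% confidence interval. The mixed-effects model already in the plan would serve.

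- Report CGAS and SAS-SR from the same model as supporting estimates, which covers the global and social functioning named in the hypothesis.
- Move C-SSRS to the safety reporting, consistent with section 3.4.
- Label the remaining methods as sensitivity analyses that cannot by themselves support the hypothesis, and give the rule for t-test versus Wilcoxon.
- Describe change over the acute phase separately.
- Reconcile the outcome list and comparison groups in the Study Summary with sections 3.3 and 7.2.

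The cost is wording and some freedom in reporting. No visits, patients or data are added. The interval may be wide, since partial responders are only part of 30, and for a pilot that width is useful information.

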7.1 Sample Size Determination

Statistical experts warn against over-interpreting pilot data for estimating power and effect sizes for larger clinical trials.⁵¹ Consequently, the proposed research study does not aim to evaluate the efficacy of the adaptive treatment strategies. Rather, the sample size was determined by the study aims which are to demonstrate the feasibility and acceptability of implementing the adaptive treatment strategies. With these aims in mind, an intent-to-treat sample size of 30 was selected. A sample size of 30 will help ensure there are enough depressed adolescents in each adaptive treatment strategy to assess feasibility and acceptability.

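### Hypothesis 5 (acute responders keep their response) is analysed only with tests of zero change, over too long a window and not in responders alone, so the planned results cannot show that response was held

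*Combined protocol and SAP*

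**What the plan says.** Under Aim 2 (Section 2), the two hypotheses make different kinds of claim. Hypothesis 5 claims maintenance: "Adolescents who were responders to acute treatment will show sustained response to continuation treatment". By contrast, Hypothesis 6 claims a gain: "Adolescents who were partial responders to acute treatment will show significant improvement in depressive symptoms and social and global functioning".

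Section 7.2 treats them as one item. "Primary analyses will examine within-subject change scores in CDRS, C-SSRS and CGAS over the course of acute and continuation treatment", by repeated measures ANOVA. Regression and ANCOVA adjusting for pre-treatment score follow, then: "The magnitudes of changes in outcomes variables over time will be assessed using the paired t-test or Wilcoxon signed-rank test for continuous variables". For patterns over time, mixed-effects models are added. No group is named for these analyses. The Study Summary describes a similar ANOVA by early and late decision point, which is not a split by response status.

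Item (3) of the same paragraph is of another kind. "Relapse will be defined as the reemergence of 5 or more symptoms of depression on the KSADS-PL", and "The percentage of adolescents who meet relapse criteria, and associated 95% confidence interval will be calculated". A recovery percentage is reported the same way.

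Section 3.3 defines a responder as CGI 1 or 2 and lists response status as a secondary endpoint. Section 7.2 names no analysis of it. On size, Section 7.1 says that "an intent-to-treat sample size of 30 was selected". The number of responders expected among the 30 is not given.

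**The concern.** A paired t-test, a signed-rank test or a repeated measures ANOVA can give evidence that scores changed. That suits Hypothesis 6. Hypothesis 5 says that nothing important was lost, and failing to find a change is not evidence for it: the smaller and noisier the group, the easier it is to find nothing. Section 7.2 does not say what sustained means, which adolescents and time window the claim is judged on, or which result would support it.

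The window adds a second problem. Responders improved during the acute phase by definition, so a test spanning both phases can show clear net improvement even if part of the gain was lost after week 16.

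At stake is whether the report can say anything reliable about maintenance in responders, the question Hypothesis 5 poses.

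**Working it through.** **No figure to reproduce.** The 30 is a feasibility choice. The documents give no alpha, power, SD of change or responder count for this hypothesis.

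**Assumptions.** Responders n = 10 to 25 of the 30 (30 shown as the extreme). Two-sided 5% test, in line with the 95% intervals used elsewhere in 7.2. True worsening δ from week 16 to week 32 in units of the SD of the change score, because that SD is among the things the study is meant to estimate.

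**1. Non-significance from week 16 onward.** With c the 97.5% point of t on n − 1 degrees of freedom, the paired t-statistic has noncentrality δ√n, and

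P(non-significant) = F(c; n − 1, δ√n) − F(−c; n − 1, δ√n),

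where F is the noncentral t distribution function. Example: n = 15, δ = 0.5 gives δ√n = 0.5 × 3.873 = 1.936, c = 2.145 and P = 0.562. The half-width of the 95% CI for the mean change is c/√n in SD units; here 2.145/3.873 = 0.55.

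| Responders | CI half-width (SD) | δ = 0.3 | δ = 0.5 | δ = 0.8 |
|---|---|---|---|---|
| 10 | 0.72 | 86% | 71% | 38% |
| 15 | 0.55 | 81% | 56% | 18% |
| 20 | 0.47 | 75% | 44% | 8% |
| 25 | 0.41 | 70% | 33% | 3% |
| 30 | 0.37 | 64% | 25% | 1% |

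The half-width is also the largest observed mean worsening that stays non-significant. With 15 responders, an observed decline of just under 0.55 SD would not reach significance.

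**2. The full span.** Change from the start of acute treatment to week 32 is A + C, with A the acute-phase change and C the change after week 16. Illustration with assumed values: an acute improvement of 2 units followed by a worsening of 0.5 leaves a net improvement of 1.5. An overall test would report improvement, although C, the only part that bears on Hypothesis 5, is a loss.

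**3. Whether item (3) fills the gap.** Its percentages are for adolescents as a whole. If 15 of the 30 were responders and three of them relapsed with no other relapses, the reported figure would be 3/30 = 10%, against 3/15 = 20% in responders. Relapse needs five or more symptoms to re-emerge, so lesser worsening is not counted. Exact (Clopper-Pearson) intervals within responders would be wide: 0 of 15 gives 0 to 22%, 2 of 15 gives 2 to 40%, and 2 of 20 gives 1 to 32%.

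**The case against.** The strongest reply is that the harmful step is nowhere written. A reader might infer that the investigators will count a non-significant result as support for Hypothesis 5. No section says so, and the sentence on magnitudes of change can be read as estimation. That stands: what is missing is a definition and an estimate, and no wrong decision rule has been stated. Over the full span, moreover, a null result in responders would mean no net improvement, which nobody would call sustained response. The misreading in step 1 arises only for a contrast starting at week 16; for the span as written, the problem is the masking in step 2.

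Second, the documents define response by CGI, so sustained response most naturally means still CGI 1 or 2. A responder's CDRS-R could rise while the CGI stays there. This is right. It makes CGI status at week 32 the natural first measure, yet 7.2 does not analyse it.

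Third, a reader might infer that deterioration would go unseen. Item (3) does not allow that reading: recovery and relapse are reported with intervals. They are partial evidence, limited as shown in step 3. Large declines would also usually be detected with 20 or more responders (missed 8% of the time or less at 0.8 SD).

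Fourth, a reader might infer that the result will settle the lighter responder schedule (4 + 2 = 6 IPT-A sessions against 8 + 2 = 10 for partial responders) in the later R01. The documents tie the R01 to Aim 3 and to the exploratory predictors and moderators, not to Hypothesis 5.

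Finally, Section 7.1 says the pilot does not set out to evaluate efficacy. That limits the weight of the point. It does not remove it, because Hypothesis 5 is stated and given an analysis.

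**Conclusion.** The point holds in limited form. As written, Section 7.2 cannot support Hypothesis 5: its tests address zero change, its stated span includes the acute-phase gain, it is not confined to responders, and it gives neither an interval for the change nor an analysis of CGI response status. With an assumed 10 to 25 responders, a true 0.5 SD worsening after week 16 would be non-significant 71% to 33% of the time, and a 0.3 SD worsening 86% to 70%. These figures rest on the assumed responder count, a two-sided 5% paired t-test and effects in SD-of-change units; whether 0.5 SD matters clinically is not settled by the documents.

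The correction is worth making because it is cheap and changes what can be concluded. It bears on a secondary conclusion and leaves the primary feasibility and acceptability endpoint untouched.

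**What to change.** In Section 7.2, separate Hypothesis 5 from Hypothesis 6 and keep the tests of change for Hypothesis 6. For Hypothesis 5, in week 16 responders only:

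- Report the percentage still CGI 1 or 2 at week 32 and the percentage relapsed, each with an exact 95% CI. Say which CGI rating is used: Section 8.4 has therapists rating at each session, while the assessment list in Section 3.1 does not name the CGI.
- Report the mean CDRS-R and CGAS change from week 16 to week 32 with 95% CIs.
- State that a non-significant change is not evidence of sustained response.
- If a yes/no criterion is wanted, set it before analysis in scale points or as a percentage. A multiple of the observed SD of change would not do: it loosens as the data get noisier. At 0.5 SD it would also leave an observed change of exactly zero inconclusive with 10 or 15 responders, where the half-widths are 0.72 and 0.55 SD.

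The cost is a few lines of text, with no extra participants or visits. The drawback is wide intervals, with half-widths of about 0.4 to 0.7 SD of the change, so the result will often be inconclusive. For a pilot of 30 that is the accurate report.
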